### 5.13. Safety Analyses

Safety measures will include hypoglycemic events, AEs/treatment-emergent adverse events (TEAEs), body weight, vital signs (systolic and diastolic blood pressures and pulse rate), treatment exposure, and laboratory measures. In general, safety summary analyses will be done for Group A+B. However, hypoglycemic event and weight analyses assessing secondary objectives will be done for both Group A and Group A+B. All safety measures will be summarized for ARS by treatment for the 26-week treatment period. If listings are provided, they will contain data after the subjects discontinue the study treatment. For treatment comparisons of frequency and proportion of event variables (such as AEs and hypoglycemia events), Fisher's exact test will be used, unless otherwise specified.

#### 5.13.1. Study Treatment Exposure

Exposure to each treatment during the treatment period of the study will be calculated for each subject and summarized by treatment group for ARS using first dosing and last dosing information. If a subject's first dosing date/time is missing, it will be replaced by the randomization date/time. If a subject's last dosing date/time is missing, it will be replaced by the last visit date/time up to discontinuation of study treatment or completion date/time (whichever is earlier). Total subject-years will be included in the summaries. The mean of exposure will be compared between treatment groups using a two-sample t-test.

#### 5.13.2. Hypoglycemic Episodes

Hypoglycemia is defined and categorized as follows:

##### Documented hypoglycemia:

- **Documented symptomatic hypoglycemia:** an event during which typical symptoms of hypoglycemia are accompanied by SMBG  $\leq 70$  mg/dL.
- **Asymptomatic hypoglycemia:** an event not accompanied by typical symptoms of hypoglycemia but with SMBG  $\leq 70$  mg/dL.
- **Unspecified or unclassifiable hypoglycemia:** an event during which SMBG  $\leq 70$  mg/dL but no information relative to symptoms of hypoglycemia was recorded.
- **Severe hypoglycemia:** an event accompanied by neuroglycopenic symptoms that results in cognitive impairment such that the patient requires assistance of another person to actively administer carbohydrates, glucagon, or perform other resuscitative actions. During these episodes, the patient has an altered mental status, and cannot assist in their care, is semiconscious or unconscious, or experienced coma with or without seizures, and may require parenteral therapy. Plasma glucose measurements may not be available during such an event, but neurological recovery attributable to the restoration of SMBG concentration to normal is considered sufficient evidence that the event was induced by a

low SMBG concentration (SMBG  $\leq 70$  mg/dL). The determination of a hypoglycemic event as an episode of severe hypoglycemia is made by the investigator.

- **Nocturnal hypoglycemia:** any hypoglycemic event (documented hypoglycemia or severe hypoglycemia) that occurs between bedtime and waking.

### 5.13.2.1. Hypoglycemic Analyses

Hypoglycemic analyses will be conducted on the ARS population. The same categories and subcategories defined in Section 5.13.2 will be used for summary and modeling purposes.

The hypoglycemic event rate (per 30 days and per 1 year), incidence (number) and percent of subjects reporting at least 1 hypoglycemic episode for a given treatment at certain week intervals will be summarized. The week intervals include: lead-in period (-2, 0], treatment period including (0, 2], (2 to 8], (8 to 26], (0 to 26] weeks. Note that the closed brackets will indicate to include a value/week; whereas, parentheses will indicate not to include the corresponding value/week. For example, (0 to 2] means all values between Week 0 and Week 2, including Week 2, but not including Week 0.

Treatment comparison of the incidence of hypoglycemia (documented [documented symptomatic, asymptomatic, and unspecified], severe, and nocturnal) will be done using logistic regression for each week interval, excluding poststudy treatment discontinuation data. For the analysis in Group A, the logistic model will include baseline hypoglycemia event rate for week interval (-2, 0] of the corresponding category of the dependent hypoglycemia variable standardized by 30 days (or 1 year) as covariates, treatment (U-500R CSII, U-500R MDI), and the stratification factors (U-500R at entry versus other insulins, entry HbA1c  $\geq 8.5\%$  or  $< 8.5\%$ ) as fixed effects. For the analysis in Group A+B, the stratification factor (and nonusers versus users of GLP-1 receptor agonists or SGLT2 inhibitors) will be added into the model.

For summary purpose, the rate per 30 days calculated between 2 visits is defined as the total number of episodes for all subjects between the visits divided by the total actual number of exposure days between the visits, and then multiplied by 30 days. A similar definition will be used to calculate the rate per subject per 365 days (1 year).

The analysis approach for the rate of hypoglycemia is based on a negative binomial model with log link function, excluding post study treatment discontinuation data. The response variable is the hypoglycemic event count per visit per subject. For Group A, the model will include baseline hypoglycemia event rate for week interval (-2, 0] of the corresponding category of the dependent hypoglycemia variable standardized by 30 days as covariates, treatment (U-500R CSII, U-500R MDI), and the stratification factors (U-500R at entry versus other insulins, entry HbA1c  $\geq 8.5\%$  or  $< 8.5\%$ ) as fixed effects. For the analysis in Group A+B, the stratification factor (nonusers versus users of GLP-1 receptor agonists or SGLT2 inhibitors) will be added into the model. The logarithm of exposure days (standardized by 30 days) between visits will be used as the offset variable. In LSMeans statement, Observed Margin (OM) option will be added to specify weighting scheme for LSMean computation as determined by the input data set. The LSMean of hypoglycemia rate per 30-days by treatment for each week interval will be reported,

and the rate ratio between treatments will also be presented. Wilcoxon signed-rank test may be performed as sensitivity analysis.

The 1-year rate of documented symptomatic and severe hypoglycemia (with BG  $\leq$ 70 mg/dL) for every 2-hour interval (0:00-1:59, 2:00-3:59, 22:00-23:59) over the 26 week post-randomization period will be summarized. The rate of hypoglycemia will also be analyzed using a negative binomial model. The response variable is the hypoglycemic event count per 2-hour interval per subject. The analysis approach will be similar to the hypoglycemia rate analysis approach above for Group A and Group A+B.

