7.1.7.1. Transition to U-500R MDI

A 2-week transition period is included in the 26-week treatment period and will follow randomization. The transition period is intended to transition all subjects safely from their current insulin regimen to U-500R TID 40:30:30 (Section [9.5](#)), and to titrate U-500R according to the TID algorithm (Section [9.8.2.1](#)). The highest 24-hour TDD from the past 3 days will be utilized for calculation of the U-500R TID dose and the dose split into the ratio of 40:30:30. Those subjects already on U-500R TID at entry can continue their pre-entry U-500R TID proportions at the discretion of the investigator. At Visit 6 through Visit 17 or ET, subjects will be treated with either U-500R CSII (Section [9.8.1.1](#)) or U-500R MDI delivered TID (Section [9.8.2.1](#)) based on titration algorithms and the treatment to which they are randomized.

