After Visit 1 (screening), subjects who meet all of the inclusion criteria (Section 8.1) and none of the exclusion criteria (Section 8.2) will remain on their pre-study treatment for a 2 week lead-in period at Visit 2 (Week -2). This lead-in period is intended to stabilize HbA1c related to study effect (Gale et al. 2007) and verify actual insulin dose. Following the lead-in, subjects will be randomized at Visit 4 (Week 0) in an open-label fashion based on a 1:1 ratio to U-500R treatment by MDI or U-500R treatment by CSII. A 2-week transition to U-500R by MDI administered T1D, regardless of insulin or combination thereof at Visit 2 (Week -2) (Section 9.5) will begin after randomization (Visit 4 [Week 0]) utilizing the T1D algorithm with weekly titrations (Section 9.8.2.1). The transition period is to ensure safe transition to U-500R insulin monotherapy from entry insulin (as applicable). After completion of the 2-week transition period, 24-weeks of U-500R delivered by MDI versus CSII will begin.

The primary and key secondary objectives will be assessed in subjects from Group A (without use of GLP-1 receptor agonists or SGLT2 inhibitors) and combined for the total study population Group A and Group B (those who use GLP-1 receptor agonists or SGLT2 inhibitors).

The study will be performed open-label since blinding of the investigators, subjects, and study site personnel could not be accomplished given the differing modes of delivery of U-500R (CSII versus MDI). To minimize bias, aggregate review of summary data by the study team (that is, CRP/CRS overseeing the global conduct of the study, statisticians, and statistical analysts) will remain blinded until after the final database is locked (Section 9.10).

8. Study Population

Individuals who do not meet the inclusion criteria for participation in this study (screen failure) may be re-screened once. The interval between screen and re-screen should be at least 2 weeks. When re-screening is performed, the individual must sign a new informed consent form (ICF) and will be assigned a new identification number.

Entered subjects who meet all inclusion criteria ([1] through [7]) and are not excluded by exclusion criteria ([8] through [28]) will initiate the lead-in period at Visit 2 (Week -2).

Prior to randomization at Visit 4, all subjects will be re-confirmed for inclusion criteria [1], [2] and [7] and exclusion criteria [18].

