9.3. Method of Assignment to Treatment

Subjects will continue on their pre-study insulin regimens until Visit 4 (Week 0). After re-confirmation of eligibility, subjects who meet specific criteria (Section 8) for enrollment will be randomized at Visit 4 (Week 0) to open-label treatment with U-500R administered by one of two treatment regimens: MDI or CSII. However, subjects randomized to CSII will not initiate U-500R administered by CSII until transition to U-500R is complete (Section 9.7). Assignment to treatment arms will be determined by a computer-generated random sequence using an IWRS.

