9.7. Transition to U-500R MDI

All subjects will administer U-500R MDI delivered TID (40:30:30 unless otherwise noted) during the transition period (Weeks 0-2). Transition to U-500R MDI will follow the criteria below in Table IBHD.9.3. Subjects will have their insulin adjusted weekly by the investigator using the algorithm from Section 9.8.2.1.

Table IBHD.9.3. Transition from entry insulin to U-500R MDI

Insulin Regimen (Screening)	HbA1c (Screening)	Mean SMBG (Screening to Week 0)	Conversion from Screening TDD to U-500R TID Dose
Insulin with or without U-500R	>8%	>183 mg/dL	1:1
Insulin with or without U-500R	>8%	≤183 mg/dL	Reduce TDD by 20%
Insulin with or without U-500R	≤8%	--	Reduce TDD by 20%
U-500R only	--	--	1:1

Abbreviations: HbA1c = hemoglobin A1c; SMBG=self-monitored blood glucose; MDI = multiple daily injections; TID= three times daily; TDD=total daily dose.

Subjects treated with U-100 and/or other concentrated insulin (with or without U-500R) at screening Visit 1 (Week -3) with HbA1c levels >8% and a mean SMBG (recorded prior to Visit 4 [Week 0]) value >183 mg/dL (corresponding to HbA1c value of >8.0% [estimated average glucose; Nathan et al. 2008]) at Visit 4 should be transitioned to U-500R using 1:1 dosage conversion.

Subjects treated with U-100 and/or other concentrated insulin (with or without U-500R) at screening Visit 1 (Week -3) with HbA1c levels >8% and a mean SMBG (recorded prior to Visit 4 [Week 0]) value ≤183 mg/dL (corresponding to HbA1c value of ≤8.0%) at Visit 4, should transition by reducing their U-500R TDD by 20%.

Subjects treated with U-100 and/or other concentrated insulin (with or without U-500R) at screening Visit 1 (Week -3) with HbA1c ≤8% should transition to U-500R at Visit 4 (Week 0) by reducing their U-500R TDD by 20%, regardless of SMBG value.

Subjects treated with U-500R insulin only at screening Visit 1 (Week -3) should transition to U-500R TID with proportion 40:30:30 using a 1:1 dosage conversion at Visit 4 (Week 0), regardless of HbA1c and/or SMBG. Those subjects already on U-500R TID at entry can continue their pre-entry U-500R TID proportions at the discretion of the investigator.

Investigators may also deviate from the proportion, if deemed necessary, for the safety or well-being of the subject (that is, due to a safety concern). Any major deviation from the recommended proportion must be discussed with Lilly CRP/CRS.

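### No hypoglycemia interval covers exactly the 24 weeks in which pump and injection differ (Weeks 2 to 26); (0 to 26] adds two weeks with both arms injecting, a modest pull toward no difference

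*SAP*

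**What the plan says.** SAP 5.13.2.1 lists a lead-in window and then "treatment period including (0, 2], (2 to 8], (8 to 26], (0 to 26] weeks". It ranks none of them. Incidence comparisons "will be done using logistic regression for each week interval, excluding poststudy treatment discontinuation data". For rates, "The LSMean of hypoglycemia rate per 30-days by treatment for each week interval will be reported", with rate ratios from a negative binomial model. A separate analysis by 2-hour clock interval is defined only over the 26 weeks after randomization. SAP 5.13 sets the general window: "All safety measures will be summarized for ARS by treatment for the 26-week treatment period".

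The Protocol fixes when the treatments diverge:

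- Section 7.1.7.1: "A 2-week transition period is included in the 26-week treatment period and will follow randomization".
- Section 9.7: "All subjects will administer U-500R MDI delivered TID (40:30:30 unless otherwise noted) during the transition period (Weeks 0-2").
- Section 9.3: "subjects randomized to CSII will not initiate U-500R administered by CSII until transition to U-500R is complete".
- Section 7.2: "After completion of the 2-week transition period, 24-weeks of U-500R delivered by MDI versus CSII will begin".

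**The concern.** Rate and incidence of hypoglycemia are secondary objectives (SAP 4.2.2), and the pump system is an investigational device (Protocol 9.2). The comparison of interest is pump versus injection, which exists only in Weeks 2-26. The one interval spanning all of that time also contains two weeks of identical delivery. Including them moves any real difference, harm or benefit, toward none. In a safety comparison, hiding an excess on the pump is the less cautious error.

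Incidence needs separate thought from rates. A subject with an event in Weeks 0-2 is already a case in (0 to 26], whatever the device does later, so the loss need not equal the 2/26 time share. The planned (2 to 8] and (8 to 26] windows are free of the transition, but they do not yield one 24-week incidence, because a subject with events in both is counted in each.

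**Working it through.** **Inputs from the documents.** Shared injection time is 2 weeks and contrast time is 24 weeks, so the shared share is 2/26 = 7.7%. Group A randomizes 320 at 1:1, or 160 per arm. The only hypoglycemia rate given is 0.1 severe episodes per patient-year, from a pump case series using its own definition (Protocol 5). The plan states no expected incidence or power for hypoglycemia, so there is no plan figure to reproduce. Its sample-size calculation concerns HbA1c only.

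**Assumptions.** Injection-arm rates run from 0.1 to 20 per year (365.25 days). The pump:injection rate ratio (RR) is 1.3 or 1.5, with 0.7 as a check. Between-subject dispersion is k = 0 (Poisson, evenly spread), 1 or 3. The Weeks 0-2 rate equals the later injection rate unless stated.

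**Rates.** The expected ratio over (0 to 26] is (2 + 24 × RR)/26.

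- RR 1.50: (2 + 36)/26 = 1.46. Log-scale loss = 1 − ln 1.4615/ln 1.5 = 6.4%.
- RR 1.30: (2 + 31.2)/26 = 1.277. Loss 6.8%.
- RR 0.70: (2 + 16.8)/26 = 0.723. Loss 9.1%.

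**Incidence.** For mean count m, P(at least one event) is 1 − exp(−m) when k = 0 and 1 − (1 + k·m)^(−1/k) otherwise. Means are rate × 24 versus rate × 24 × RR weeks for (2 to 26], and rate × 26 versus rate × (2 + 24 × RR) weeks for (0 to 26]. Loss is 1 minus the (0 to 26] contrast divided by the (2 to 26] contrast.

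Worked case, 5 per year, RR 1.5, k = 1:

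- (2 to 26]: means 5 × 168/365.25 = 2.300 and 3.450; incidences 69.7% and 77.5%.
- (0 to 26]: means 5 × 182/365.25 = 2.491 and 5 × 266/365.25 = 3.641; incidences 71.4% and 78.5%.
- The difference falls from 7.8 to 7.1 points (9.4% loss). With k = 1 the odds equal the mean, so the odds ratio falls from 1.50 to 1.46 (6.4% on the log scale).

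Loss at RR 1.5, risk difference / log odds ratio:

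| Rate per year | k = 0 | k = 1 | k = 3 |
|---|---|---|---|
| 0.1 | 0.4% / 6.2% | 0.7% / 6.4% | 1.3% / 6.7% |
| 1 | 3.8% / 4.8% | 4.7% / 6.4% | 5.4% / 7.4% |
| 5 | 17.4% / 1.1% | 9.4% / 6.4% | 7.6% / 7.4% |
| 20 | 53.5% / 0.0% | 11.6% / 6.4% | 8.2% / 7.1% |

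At RR 1.3 the log-odds-ratio loss is 0-8.0%, and the risk-difference loss at 5-20 per year with k = 1-3 is 8-12%. At RR 0.7 the log-odds-ratio loss reaches 10.6% and the risk-difference loss with k = 1 reaches 15.7%. Under Poisson the risk-difference loss equals the share of subjects with an event in Weeks 0-2, which is why it grows when events are common and evenly spread.

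**Precision.** With 160 per arm, the Wald z was smaller for (0 to 26] in every scenario. The power lost was at most about 10 points at k = 0 and about 6 points at k = 1-3.

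**Transition rate not constant.** If the Weeks 0-2 rate is 2 or 3 times the later injection rate, the log-odds-ratio loss at RR 1.3-1.5 and k = 1-3 is about 12-15% or 17-21%. At RR 1.3 and half the later rate it is at most 4%.

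**The case against.** The SAP already isolates the problem. (0 to 2] shows the transition alone, (8 to 26] covers 18 of the 24 contrast weeks, and (2 to 8] covers the other 6. Both incidence and rate are modelled in each. Crude (2 to 26] rates can be rebuilt, since events and exposure add. Hypoglycemia lies outside H1-H10, no decision rule depends on (0 to 26], severe events are also listed as serious adverse events, and a data monitoring committee sees unblinded safety data. Moreover (0 to 26] starts at randomization. Allocation is open from Week 0, so (2 to 26] conditions on staying on treatment after the arm is known.

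All of this stands, and it argues for keeping (0 to 26]. It does not supply a single 24-week incidence or model estimate, and the 2-hour analysis has no transition-free version.

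Two stronger readings are tempting. The first is that (0 to 26] is the SAP's principal interval; the SAP does not say so. The second is that incidence is diluted far beyond 2/26. That follows if, say, 20% or 40% of subjects have an event in Weeks 0-2 against 35% of the injection arm in Weeks 2-26. The injection arm is on the same injection regimen in both periods, and −ln(0.65)/24 = 0.0179 per week. Reaching 20% or 40% in two weeks needs −ln(0.8)/2 = 0.112 or −ln(0.6)/2 = 0.255 per week, which is 6.2 or 14.2 times that rate. The documents give nothing to support this. At a constant rate, 1 − 0.65^(2/24) = 3.5% have an early event. Combining that independently with 35% versus 50% over 24 weeks gives 37.3% versus 51.8%. The 15-point difference becomes 14.5, the odds ratio moves from 1.86 to 1.80, and the log-odds-ratio loss is 4.6%, below 7.7%.

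**Conclusion.** The gap is real: the plan has no (2 to 26] interval, and both (0 to 26] and the 2-hour analysis carry two weeks of identical delivery that bias a true difference toward none. Its expected size is modest. With a constant injection rate, the loss is about 6% on the log scale for a rate ratio of 1.5 and about 0-8% on the log odds ratio, the scale of the SAP's incidence model, at rate ratios of 1.3-1.5. For severe events at 0.1 per year, the risk difference loses about 1% or less.

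The loss is larger in two situations. One is the risk difference for common categories, about 8-12% with between-subject variation and 17-54% if events at 5-20 per year are evenly spread. This matters because the SAP also reports percentages, which readers will compare directly. The other is clustering of events in the transition. Every subject changes regimen or has doses reviewed then, so a constant rate cannot be taken for granted, but the documents give no rate for that period. All rates except 0.1 per year, and all rate ratios and dispersions, are assumptions. This is a cheap improvement to a safety analysis and does not touch the controlled efficacy tests.

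**What to change.** Add a pre-specified (2 to 26] week interval in SAP 5.13.2.1 to the logistic models for incidence, the negative binomial models for rate, and the 2-hour-interval analysis, for Group A and Group A+B. Report it beside (0 to 26], which stays as the all-randomized comparison. State in advance that (2 to 26] addresses the pump-versus-injection contrast, so that the choice of interval is not made after unblinding.

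The cost is one more interval in tables and models already planned, with no new data. The downside is that subjects who leave treatment before Week 2 do not contribute to (2 to 26], so it no longer compares everyone randomized. Showing both rows, with the number contributing to each, makes that visible.

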12.2.10. Safety Analyses

As stated in Section 6.2, all of the secondary objectives will be analyzed for Group A and for the total study population (Groups A and B combined). Safety measures will include hypoglycemic events, body weight, AEs and TEAEs, vital signs (systolic and diastolic blood pressures and pulse), study treatment exposure, and laboratory measures. As stated in Section 12.2.1, all safety measures will be summarized for ARS including the data after subjects discontinue study treatment and device but still remain in the study by treatment and by visit for the 26-week treatment period. Safety measures will also be listed for those patients who discontinue study treatment but still remain in the study for safety monitoring purpose. These listings will contain data after the patients discontinue the study treatment. For treatment comparisons of frequency and proportion of event variables (such as AEs and hypoglycemia events), the conventional Fisher’s exact test or Pearson’s chi-square test are appropriate to use. Further details of analyses will be provided in the SAP.

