12.2.10.1. Hypoglycemia

The rate per 30 days calculated between 2 visits is defined as the total number of episodes for all subjects between the visits divided by the total actual number of exposure days between the visits, and then multiplied by 30 days. A similar definition will be used to calculate the rate per subject per 365 days (year).

For documented (documented symptomatic, asymptomatic and unspecified), severe and nocturnal hypoglycemic episodes, the following analyses will be conducted. The incidence and percentage of subjects with at least 1 hypoglycemic event will be analyzed using Fisher’s exact test or Pearson’s chi-square test, as appropriate. The rate of hypoglycemic events per 30 days

and per 365 days will be analyzed using a negative binomial regression model with similar fixed effects as in the primary MMRM analysis model. Baseline hypoglycemic event rate for the corresponding category of the dependent hypoglycemia variable will be included as a covariate, as well as the stratification factors.

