Separate efficacy analyses for primary and key secondary objectives will be conducted by either including or excluding post study treatment discontinuation data based on different purposes (see Section 5.9 and Section 5.10). In general, missing data will not be imputed, unless otherwise specified, for example, where the Last-Observation-Carried-Forward (LOCF) method or the copy reference multiple imputation method (per FDA's request) is mentioned.

Outcomes (laboratory, vital signs, weight, patient reported outcome questionnaires) measured within 5 days of last treatment dose will be considered on treatment and included in the analysis during the treatment period.

For data collected as a running record with an exact date stamp such as adverse events (AEs), SMBG, and hypoglycemia event where the dates of the measures were not tied with the date of an office visit, post-baseline data recorded at or prior to the last study drug dose date will be considered as data on treatment and included in the analysis during the treatment period.

Baseline will be the last value obtained at or prior to the randomization, unless otherwise stated.

For continuous measurements, summary statistics will include sample size, mean, median, SD, minimum, and maximum. Summary statistics for continuous measures will be provided for baseline, the actual measurements at each visit, and the change from baseline measurements to each visit. For all continuous variables, both the actual value and change from baseline (if available) will be analyzed.

An MMRM model will be used for continuous outcomes with repeated post-baseline measurements to compare treatment arms, unless otherwise noted. An ANCOVA or analysis of variance (ANOVA) model may also be used for continuous outcomes to compare treatment arms at the endpoint using the LOCF method. Treatment comparisons will be performed for the treatment difference in least squares means (LSMean). LSMean (standard error [SE]) by treatment group and visit (if applicable), the LSMean difference between treatment groups, along with 95% confidence limits of the treatment differences and the p-value for the treatment comparison will be displayed. For the change from baseline, p-value for the within-treatment difference will also be displayed.

All tests of treatment effects will be conducted at a 2-sided alpha level of 0.05, unless otherwise stated.

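### Hypoglycemia incidence is compared on data cut at treatment discontinuation with no term for time observed, so unequal discontinuation biases the proportion of subjects with an event

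*SAP*

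**What the plan says.** Rate and incidence of hypoglycemia together form one of the other secondary objectives (SAP 4.2.2). SAP 5.13.2.1 sets the population: "Hypoglycemic analyses will be conducted on the ARS population". That set keeps subjects who stopped treatment early (SAP 5.2).

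Incidence means at least one event, yes or no. Its comparison "will be done using logistic regression for each week interval, excluding poststudy treatment discontinuation data". The intervals are the "treatment period including (0, 2], (2 to 8], (8 to 26], (0 to 26] weeks". The model takes the baseline event rate of the same category "as covariates, treatment (U-500R CSII, U-500R MDI), and the stratification factors". No exposure term, offset or time-to-event method is listed. For hypoglycemia records SAP 5.2 puts the cut at the last dose: "post-baseline data recorded at or prior to the last study drug dose date will be considered as data on treatment".

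The event-rate model, also in 5.13.2.1, is a negative binomial regression on the same cut, but it allows for time: "The logarithm of exposure days (standardized by 30 days) between visits will be used as the offset variable".

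The protocol differs on both data and method. Section 12.2.10 states that "all safety measures will be summarized for ARS including the data after subjects discontinue study treatment and device but still remain in the study". Section 12.2.10.1 states "The incidence and percentage of subjects with at least 1 hypoglycemic event will be analyzed using" Fisher's exact or Pearson's chi-square test.

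**The concern.** In the model for Weeks 0 to 26, a subject who stopped at Week 3 without an event is recorded as the same non-event as a subject followed event-free for 26 weeks. For the first subject, no event partly means not observed. Cutting follow-up can only remove first events and never adds them. If one arm loses more on-treatment time, its odds of an event fall for a reason unrelated to hypoglycemia risk.

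Unequal loss is plausible in an open-label comparison of a pump with injections. Treatment can be stopped for poor compliance or for more than 7 days off drug (Protocol 8.3.2), and compliance is judged partly on use of the assigned delivery method (Protocol 9.12). At stake is a safety comparison that would flatter whichever arm retains fewer subjects on treatment.

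**Working it through.** **The plan's own figures.** Noninferiority sample size: 2 × (1.960 + 0.842)² × 1.1² / 0.4² = 118.7, so 119 per arm or 238 in total, which agrees with the stated 240 completers. Randomized: 240 / (1 − 0.25) = 320, or 160 per arm in Group A. The 25% is pooled. The documents give no per-arm discontinuation and no planning incidence for any hypoglycemia category. The only background figure is 0.1 episodes per patient per year for severe events in a pump case series, under that series' own definition (Protocol 5).

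**Assumptions, not in the documents.** True event rates are equal in both arms. Discontinuation d is 25/25, 30/20 or 35/15%, each averaging the stated 25%. Rates r run from 0.1 to 30 per year. In the second and third checks below, events are either Poisson or overdispersed (negative binomial, dispersion 1).

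**Check 1: everyone who stops does so at week w, constant rate.** With I the full 26-week incidence and λ = −ln(1 − I)/26, the observed incidence in an arm is (1 − d)·I + d·(1 − exp(−λw)).

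For I = 60% and w = 6, the last bracket is 1 − 0.4^(6/26) = 0.191.
- Arm losing 30%: 0.7 × 0.60 + 0.3 × 0.191 = 47.7%
- Arm losing 20%: 0.8 × 0.60 + 0.2 × 0.191 = 51.8%
- Odds ratio: (0.477/0.523) / (0.518/0.482) = 0.85

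At w = 10 and w = 13 the odds ratio is 0.89 and 0.91. At 35/15, with I from 60 to 80% and w from 6 to 13, it runs from 0.64 to 0.83. Equal discontinuation gives 1.00.

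**Check 2: stopping times uniform over 26 weeks.** Observed incidence is (1 − d)·F(T) + d·(mean of F over 0 to T), with T = 26/52.18 years and F(t) = 1 − exp(−rt) or, overdispersed, 1 − 1/(1 + rt). Rejection is the chance that a two-sided 5% Wald test with 160 per arm finds a difference.

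| r per year | Events | 30/20: incidence, OR, rejection | 35/15: incidence, OR, rejection |
|---|---|---|---|
| 0.1 | Poisson | 4.14 vs 4.38%, 0.943, 5.1% | 4.02 vs 4.50%, 0.888, 5.5% |
| 2 | Poisson | 55.17 vs 57.81%, 0.898, 7.6% | 53.85 vs 59.13%, 0.807, 15.8% |
| 2 | Overdispersed | 44.13 vs 46.05%, 0.925, 6.4% | 43.16 vs 47.02%, 0.856, 10.7% |
| 12 | Poisson | 94.82 vs 96.46%, 0.671, 11.0% | 94.00 vs 97.28%, 0.437, 28.9% |
| 12 | Overdispersed | 80.22 vs 82.04%, 0.888, 7.0% | 79.31 vs 82.95%, 0.788, 13.2% |

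For rare events the odds ratio is close to the ratio of time observed: (1 − 0.35/2)/(1 − 0.15/2) = 0.825/0.925 = 0.892. At 30/20 with overdispersed events, the odds ratio stays between 0.865 and 0.943 over all rates tried. The very low Poisson values at 12 per year arise where nearly everyone has an event, so a small difference in percentage points makes a large odds ratio. As an extreme of timing, if everyone stops at Week 2 (35/15, Poisson, r = 2), incidence is 43.6 vs 54.7% and the odds ratio 0.64.

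**Check 3: the interval from Week 8 to Week 26.** Suppose all discontinuation precedes Week 8 and those subjects are kept as non-events. With 26-week incidence 60%, the chance of an event in the 18 weeks is 1 − 0.4^(18/26) = 0.470.
- 30/20: 0.7 × 0.470 = 32.9% vs 0.8 × 0.470 = 37.6%, odds ratio 0.81
- 35/15: odds ratio 0.66

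If those subjects are left out of that interval, this part of the bias disappears.

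**Check 4: does allowing for exposure remove it?** Simulation at 35/15 with equal true rates (r = 0.5, 2 and 12; 1000 trials per scenario):

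| Model | Median ratio | Rejection |
|---|---|---|
| Logistic, as written | 0.43 to 0.88 (OR) | 6.2 to 24% |
| Complementary log-log with log time offset | 0.98 to 1.06 | 3.8 to 5.8% |
| Negative binomial with exposure offset, dispersion known | 0.99 to 1.01 | 3.7 to 5.5% |

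**The case against.** The case against acting has several parts.

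- **The rate model is already right.** A reader might infer that the arm losing more subjects will show fewer events. The documents do not support that: event counts are compared with an exposure offset for each week interval. This stands and confines the point to the proportion of subjects with an event. It does not cure that proportion, which is a separate part of the objective.
- **The imbalance is assumed.** Only a pooled 25% is given. A reader might infer that the bias will favor the pump. Nothing in the documents says which arm will lose more time, or that either will. This stands, and the size is therefore conditional.
- **Early stoppers may not be counted as event-free in later intervals.** SAP 5.13.2.1 gives no denominator rule, so the reading in which they are is an inference for Weeks 8 to 26. For Weeks 0 to 26 it is not, because these subjects have data in that interval. The first two intervals are short, and both arms inject until Week 2 (Protocol 9.7), so pump use cannot drive losses before then.
- **Discontinuation after hypoglycemia comes too late to matter.** Recurrent hypoglycemia is a named reason for leaving the study (Protocol 8.3.3), but the event has been counted by then. This weakens the effect where that is the reason for stopping.
- **Readers will see any imbalance.** Exposure is compared between arms (SAP 5.13.1), as are reasons for discontinuation (SAP 5.4). That warns the reader but supplies no corrected estimate.
- **A constant rate is doubtful under intensive titration to Week 14.** With the early hazard set at 0.5 to 3 times the later one, the complementary log-log model with offset gave ratios of 0.97 to 1.05, against logistic odds ratios of 0.70 to 0.95. The objection is fair in principle but small in effect.

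**Conclusion.** The point holds for the proportion of subjects with at least one event. It matters mainly for Weeks 0 to 26, and for Weeks 8 to 26 only if earlier stoppers are kept as non-events. The direction is certain when true rates are equal: the arm with less on-treatment time shows the lower incidence.

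The size rests on assumed splits and rates. It is nil when amount and timing of discontinuation match. It is modest at 30% versus 20% (odds ratio roughly 0.85 to 0.95, lower only when almost everyone has an event or stopping is very early). It is larger at 35% versus 15% (roughly 0.64 to 0.90 for common events, with the same exceptions). For severe events at 0.1 per year it is about half a percentage point even at 35% versus 15%, with rejection at 5.5%.

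A reader might also infer a threat to the trial's error control. There is none: incidence lies outside the H1 to H10 family, so the primary and key secondary conclusions are untouched. What is at risk is a biased safety comparison within a named secondary objective. That warrants a change to the SAP, though not an urgent one.

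**What to change.** In SAP 5.13.2.1:

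1. Base the treatment comparison of incidence on a model that allows for time observed, with the covariates already listed. Use either a binary model with complementary log-log link and log on-treatment days in the interval as offset, or time to first event censored at last dose. Report the ratio with its 95% confidence interval.
2. State the denominator: a subject with no on-treatment day in an interval leaves that interval's model.
3. Keep the crude percentages as description, and the logistic odds ratio too if wanted.
4. Reconcile with Protocol 12.2.10 and 12.2.10.1. State which test and which data cut carry the comparison, and whether an analysis that keeps data after discontinuation is reported beside it.

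The cost is a few lines of wording and a link or offset option, since exposure days are already derived for the rate model. The estimate becomes a ratio of first-event rates or hazards in place of an odds ratio. The offset version assumes a roughly constant rate within the interval; the time-to-event version does not. Both still assume that, given the covariates, stopping treatment is unrelated to the risk of a first event.
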